### **9.2.3 Removal of subjects from the study**

A patient can be withdrawn from the study for the following reasons:

1. A patient withdraws consent, without the need to justify the decision.
2. The patient was erroneously included in the study.

Boehringer Ingelheim (BI) reserves the right to discontinue the study overall or at a particular study site at any time for the following reasons:

1. Failure to meet expected enrollment goals overall or at a particular study site
2. Emergence of any efficacy/safety information that could significantly affect continuation of the study,
3. Violation of applicable sections of Good Clinical Practice (GCP), Good Pharmacoepidemiology Practice (GEP), the study protocol, or the contract by a study site or investigator.

The investigator / the study site will be reimbursed for reasonable expenses incurred in case of study termination (except in case of the third reason).

### 9.2.4 Visit schedule

Collection of data in the study should be managed during routine practice visits or through telephone contacts with the patient, and follow the schedule in Table [9.2.4:1](#) as closely as possible.

Table 9.2.4:1 Schedule of data collection time-points

	Baseline	At hospital discharge (or 14 days) 	3 months	6 months	12 months
All patients	X	X			
DE or VKA patients followed for 1 year (objective 2 only)	X	X	X	X	X

1. Data will be collected at the date of hospital discharge or at 14 days post diagnosis, whichever is later.

#### Baseline

The “baseline” procedures and data to be collected may be done in one visit or over a series of contacts occurring after the acute VTE event based on information in the patient’s medical record and/or information that is reported by the patient. Treatment with some NOACs (e.g., dabigatran etexilate or edoxaban) requires 5 to 10 days of pre-treatment with parenteral therapy; therefore, additional data will be collected according to the flowcharts (Table [9.3.1:1](#) and [9.3.1:2](#)) at hospital discharge or 14 days after baseline, whichever is later.

#### Follow-up

Only patients who are treated with dabigatran etexilate or VKA are eligible to participate in the second objective that will include follow-up for up to 12 months after the index event. Balanced enrollment should be followed with regards to the treatment (i.e., dabigatran etexilate or VKA) and the type of index event (e.g., DVT or PE or DVT and PE). The decision to enroll a dabigatran etexilate or VKA patient for follow-up should be made as soon as the dabigatran etexilate or VKA has been prescribed and the patient has signed the study informed consent form (in accordance with local regulations). Patients should not be excluded from participation due to early outcome events (e.g., bleeding events). Data from all visits conducted under usual practice should be recorded in the electronic data capture (EDC) system at each data collection time-point even if the patient stops or changes treatment for the VTE event. Follow-up should be conducted by in-person clinic visits ideally. However, if no follow-up clinic visit occurs as part of clinical practice within one month of the planned data collection time-point (refer to Table [9.3.1:2](#)), then follow-up contact with patient will be done by telephone, and email, if available.

If a patient discontinues the study for any reason, a follow-up assessment should be performed at the time of study discontinuation, if possible.

If the treatment for a patient changes during the study the following guidance should be followed:

- An objective 1 patient whose anticoagulation treatment is switched to DE or VKA can be enrolled into objective 2 as long as inclusion criteria 2 and 4 are met
- An objective 2 patient whose anticoagulant treatment is switched will be followed-up per protocol, including ePROs
- An objective 2 patient who stops taking anticoagulation treatment will be followed-up per protocol but will discontinue ePROs.

### 9.3 VARIABLES

#### 9.3.1 Data points

Table 9.3.1:1 Flowchart for Objective 1

Data collection time point	Baseline	At hospital discharge (or 14 days)
Informed consent	X	
Review of in- / exclusion criteria	X	
Demographics	X	
Medical history	X	
VTE disease characteristics	X	X
Treatment for VTE	X	X
Height	X	
Weight	X	
Blood pressure and heart rate	X	
Collect Laboratory data (if available)	X	
Adverse drug reactions (ADR) 	X	X
Adverse events with fatal outcomes 	X	X
Concomitant therapy	X	
Completion of patient participation		X

1. Data will be collected at the date of hospital discharge or at 14 days post diagnosis, whichever is later.
2. For collection and reporting of ADRs and AEs with fatal outcome please refer to [Section 11.2.](#)

Table 9.3.1:2 Flowchart for Objective 2

Data collection time point	Baseline	At hospital discharge (or 14 days) 	3 months	6 months	1 year
Informed consent	X				
Review of in- / exclusion criteria	X				
Demographics	X				
Medical history	X				
VTE disease characteristics	X	X			
Treatment for VTE	X	X	X	X	X
Concomitant diseases		X	X	X	X
Height	X				
Weight	X		X	X	X
Blood pressure and heart rate	X				
Collect Laboratory data (if available)	X	X	X	X	X
Adverse drug reactions (ADR) 	X	X	X	X	X
Adverse events with fatal outcomes 	X	X	X	X	X
Outcome events	X	X	X	X	X
Morisky Medication Adherence Scale			X	X	X
Health resource utilization			X	X	X
PACT-Q2			X	X	X
Concomitant therapy	X	X	X	X	X
Completion of patient participation					X
Vital status collection 			X	X	X

1. Data will be collected at the date of hospital discharge or at 14 days post diagnosis, whichever is later
2. For collection and reporting of ADRs and AEs with fatal outcome please refer to [Section 11.2.](#)
3. Vital status will be collected if the patient declines further clinic visits. See also [9.3.3.](#)

#### 9.3.1.1 Baseline visit data points

The Flowchart (Table [9.3.1:1](#) and Table [9.3.1:2](#)) outlines all of the data points to be collected. No study procedures or data recorded in the EDC system should be performed unless the patient has consented to participate in the study or a waiver has been obtained in accordance with local regulations. As in any observational study, patients will be managed according to local clinical practice. The choice of treatment is solely at the discretion of the participating physicians. This means there are no additional medical or procedural risks to patients by

participating in this study. No additional medical procedures are required, over and above those that the patient would receive if not enrolled.

- Review of in- and exclusion criteria
- Demographic data will include year of birth, gender, race (as allowed by local regulations), insurance status
- Height, weight, blood pressure, and heart rate
- Available laboratory data (e.g., serum creatinine, hemoglobin, and INR)
- Information regarding the index VTE event including:
  - date of diagnosis,
  - risk factors for VTE (i.e., if the VTE was provoked or unprovoked),
  - clinical signs and symptoms and
  - the following variables based on objective testing (e.g. Venous compression ultrasonography, venography for DVT CT, MRI and any other examination that is deemed relevant per routine clinical practice for DVT diagnosis or ventilation-perfusion (V-Q) lung scan, pulmonary angiography or spiral (helical) computed tomography scan for PE):
    - Date of diagnostic testing
    - Location, extent and severity of venous thrombus
    - Impression or findings
- Treatment for VTE should include all treatment details including specific therapies provided for the event, start date(s) and stop dates (if applicable), dosage, planned treatment duration, and rationale for treatment choice.
- Medical history including current concomitant diseases, history of previous VTE (if any) risk factors (i.e., if the VTE was provoked or unprovoked) for VTE re-occurrence and risk factors for bleeding.
- Concomitant therapies that are being currently used by the patient including the name of the therapy and indication.

9.3.1.2 Hospital discharge or at 14 days after diagnosis of VTE event (whichever occurs later)

For [Objective 1](#), the additional data points will include:

- Any changes to the treatment for the VTE event
- Date of hospital discharge, if patient was admitted to hospital

For [Objective 2](#), the additional data points will include:

- Any changes in VTE disease characteristics and/or treatment for the VTE event
- Concomitant diseases (current, any changes)
- Available laboratory data that is associated with outcome events (e.g., complete blood count (CBC) for major and clinically relevant non major bleeding events)
- INR for VKA patients
- Date of hospital discharge, if patient was admitted to hospital.
- Changes in concomitant therapies
- Information on any outcome events that may have occurred since study enrollment
- Adverse drug reactions

### 9.3.1.3 Follow-up visit data points

The flowchart ([Table 9.3.1:2](#)) outlines all of the data points to be collected for patients who are followed.

- Type of data collection (i.e., based on routine clinic visit or telephone contact)
- Concomitant diseases (current, any changes)
- Available laboratory data that is associated with outcome events (e.g., CBC for major and clinically relevant non major bleeding events)
- INR for VKA patients
- Anticoagulation treatment (current, any changes (start or stop dates) including adherence, reasons for dose change). Adherence will be assessed using the Morisky Medication Adherence Scale (refer to the [Annex 3.1](#)).
- Changes in concomitant therapies
- Information on any outcome events that may have occurred since the previous visit. If the specific reversal agent for dabigatran is given, information surrounding the clinical circumstances, treatment, and clinical outcome will be collected on the CRF.
- Adverse drug reactions
- PACT-Q2 to be completed by the patient (collection of the PACT-Q2 should occur as close to the data collection time-point as possible). Refer to the [Annex 3.2](#).
- Details of health care resources utilization including:
  - Date, reason and duration of hospitalization occurring
  - Date and reason for visit to ER
  - Need to visit treating physician due to recurrent VTE event, bleeding event or for dose adjustment of anticoagulant therapy
  - For patients treated with VKA only:
    - The number of INR measurements and where the INR blood samples were drawn (e.g., physician's office, anticoagulation clinic, hospital, outpatient laboratory, self-monitoring)
    - At the 3 month data collection time-point *only*, the following details should be collected:
      - The distance traveled to have the INR measured
      - The time spent traveling to have the INR measured
      - If public transportation was used
    - If private transportation was used

### 9.3.2 Outcome measures

For [Objective 1](#):

The following primary outcome measures will be analyzed on data that is collected at the time of the acute VTE event:

- Demographic information (age and gender)
- VTE event information (event type and treatment for event)

The following further outcome measures will be analyzed on the collected baseline data:

- co-medication
- co-morbidities,

- basic physical examination data
- laboratory information
- VTE event information including location, extent and severity of the thrombus
- VTE risk factors
- history of VTE event
- bleeding risk

For [Objective 2](#):

The following primary outcomes will be analyzed from time of diagnosis of the index event to 12 months post diagnosis:

- Primary safety outcome measure: ISTH Major bleeding and ISTH clinically relevant non major bleeding (CRNMB)
- Primary effectiveness outcome measure: symptomatic recurrent VTE including VTE-related mortality

The following secondary outcomes will be analyzed from the time of diagnosis of the index event to 12 months post diagnosis:

- Recurrent DVT and/or PE
- VTE-related mortality
- All-cause mortality

The following further outcomes will be analyzed from time of diagnosis of the index event to 12 months post diagnosis:

- Life-threatening bleeding events
- Acute coronary syndrome (ACS)
- Serious adverse drug reactions
- Net clinical benefit (NCB)
- Satisfaction with anticoagulation treatment (PACT-Q2)
- Health care resource utilization

### **9.3.3 Assessment of outcome measures**

Major bleeding, defined as meeting one or more of the following ISTH criteria [[R05-0344](#), [P11-05406](#)]:

- Overt bleeding associated with a reduction in hemoglobin of at least 20 grams per liter or leading to a transfusion of at least 2 units of blood or packed cells
- Symptomatic bleeding in a critical area or organ: intraocular, intracranial, intraspinal, or intramuscular with compartmental syndrome, retroperitoneal bleeding, intra-articular bleeding or pericardial bleeding

Life-threatening bleeding, as defined as meeting one or more of the following criteria:

- Symptomatic intracranial bleed
- Reduction in hemoglobin of at least 50 grams per liter

- Transfusion of at least 4 units of packed cells, associated with hypotension requiring the use of intravenous inotropic agents
- Necessitated surgical intervention
- Fatal bleeding

Clinically relevant, non-major bleeding, defined as meeting one or more of the following ISTH criteria [[P15-12889](#)]

- Any sign or symptom of hemorrhage (e.g., more bleeding than would be expected for a clinical circumstance, including bleeding found by imaging alone) that does not fit the criteria for the ISTH definition of major bleeding but does meet at least one of the following criteria:
  - requiring medical intervention by a healthcare professional
  - leading to hospitalization or increased level of care
  - prompting a face to face (i.e., not just a telephone or electronic communication) evaluation

Recurrent DVT and/or PE: All recurrent VTE require objective verification by definitive diagnostic evaluation:

- any suspected DVT must be confirmed by venous compression ultrasonography conventional venography, CT or MRI to be entered as recurrent DVT in the CRF
- any suspected PE must be confirmed by one of the following: V-Q lung scan, pulmonary angiography, or spiral (helical) CT to be entered as recurrent DVT in the CRF

Deaths: Deaths will be classified as being:

- bleeding related (including bleeding events that contributed to deaths),
- VTE related (including VTE events that contributed to death based on investigator clinical judgment) and
- other.

ACS: will include ST elevation myocardial infarction (STEMI), non-STEMI (NSTEMI) and unstable angina (UA) [[P13-10618](#)].

- STEMI: must have cardiac marker evidence of myocardial necrosis (e.g. positive cardiac troponin (Tn) or creatinine kinase isoenzymes CKM and CKB (CK-MB)) and new (or presumably new, if no prior electrocardiogram (ECG) is available) ST segment elevation or left bundle branch block on admission ECG.
- NSTEMI: will have cardiac marker evidence of myocardial necrosis (positive Tn or CK-MB) without new ST segment elevation.
- UA: is angina pectoris with any 1 of the 3 following features:
  - Angina occurring at rest and prolonged (usually  $\geq 10$  min)
  - New-onset angina of at least Canadian Cardiovascular Society (CCS) classification III severity
  - Recent acceleration of angina reflected by an increase in severity of at least 1 CCS class to at least CCS class III. The patient must also not have any biochemical evidence of necrosis.

Serious adverse drug reactions: refer to Section [11.1](#) and [11.2](#) for serious criteria and reporting requirements.

NCB: the event rate of recurrent symptomatic VTE or VTE-related mortality plus the major bleeding event rate will be compared for dabigatran etexilate versus VKA. [[P14-17361](#)]

Treatment adherence: adherence will be assessed using the [Morisky Medication Adherence Scale](#).

Treatment persistence: will be assessed as time from treatment onset until permanent treatment discontinuation.

Exposure: will be assessed based on the anticoagulation treatment start date, dosage and the reported end date.

Perception of anticoagulation treatment satisfaction will be assessed using the PACT-Q2 (administered at follow-up time-points for those patients followed under [Objective 2](#)).

Health care resource utilization will be assessed as number of hospital admissions, emergency room visits, and physician's office visits calculated per-patient-per-month to account for variable follow-up time.

Vital status: if a patient is enrolled for follow-up ([Objective 2](#)) and then declines to return for clinic visits, the patient's vital status should be collected and reported after one year. If any outcome events (e.g., bleeding events, recurrent VTEs or other adverse drug reactions (ADRs)) occur, details should be recorded in the electronic Case Report Form (eCRF) and reported as appropriate. If the patient died, available data (e.g. date of death, cause of death) should be reported.

## **9.4 DATA SOURCES**

RE-COVERY is a study based on new data collection. Data will be collected based on assessment of the patient (e.g., physical examination and patient interview), review of hospital / medical records and available laboratory and diagnostic test reports. Patient reported outcomes will be assessed using validated questionnaires. Refer to Section [9.10.2.1](#) for details regarding source documents.

## **9.5 STUDY SIZE**

For [Objective 1](#):

It is planned that a total of approximately 6000 patients will be enrolled. This is not based on formal sample size calculations as there are no hypotheses to be tested. If eligible, patients included in the cross-sectional assessment (Objective 1) who are treated with dabigatran etexilate and a similar number of those treated with VKA will be followed ([Objective 2](#)).

Baseline demographics and characteristics of the patient population will be described by estimates and confidence intervals (CI) overall and by relevant categories as specified in Section [9.7](#) and the statistical and epidemiological analysis plan SEAP. Categorical attributes will be estimated with the precision (i.e., width of descriptive 95% CI) described in Table [9.5:1](#), according to sample size and prevalence of the attribute.

Table 9.5:1 Width of 95% CI by sample size and prevalence of attribute

Prevalence of attribute	Sample size (overall or per subgroup)					
	500	1000	2000	3000	4000	6000
5% Expected n	25	50	100	150	200	300
95% CI width	4.03	2.81	1.96	1.59	1.38	1.12
10% Expected n	50	100	200	300	400	600
95% CI width	5.46	3.82	2.68	2.18	1.88	1.54
20% Expected n	100	200	400	600	800	1200
95% CI width	7.20	5.05	3.55	2.90	2.50	2.04
30% Expected n	150	300	600	900	1200	1800
95% CI width	8.21	5.77	4.06	3.28	2.86	2.34
40% Expected n	200	400	800	1200	1600	2400
95% CI width	8.77	6.17	4.34	3.54	3.06	2.49
50% Expected n	250	500	1000	1500	2000	3000
95% CI width	8.94	6.29	4.43	3.61	3.12	2.54

\* Calculations are based on the Clopper-Pearson method.

For example, if an attribute has a prevalence of 40% in the population of acute VTE patients, with a sample size of 2000 patients, this proportion can be estimated with a precision of 4.34% (i.e. width of 95% CI). Furthermore, in a subgroup that consists of 1000 patients, this same proportion can be estimated with a precision of 6.17%.

For [Objective 2](#):

Baseline data will be summarized descriptively for eligible patients using a similar approach as described above for Objective 1. Categorical attributes will be estimated with the precision described in Table 9.5:1. For example, a sample size of 2000 patients allows a population attribute with a 30% prevalence to be estimated with a precision of 4.06%.

The primary and further outcomes will be analyzed for dabigatran etexilate patients in comparison to VKA patients over 1 year. To support the sample size determination, assessments were performed for the primary safety outcome of major and clinically relevant non-major bleeding based on the observed event rate for VKA in the pooled analysis of the RE-COVER and RE-COVER II trials, and additional assumptions including a 1:1 ratio of dabigatran etexilate and VKA patients, one-year fixed follow-up, one-sided alpha of 0.025, and 15% loss to follow-up (Table [9.5:2](#)). With these assumptions, a total sample size of 5000

patients would provide 90% power to detect a hazard ratio of 0.69 between dabigatran etexilate and VKA.

Table 9.5:2 Sample size assessments for the primary safety outcome of major and clinically relevant non-major bleeding

Event rates		Hazard ratio	Power	Loss to follow-up	Total N
Dabigatran etexilate	VKA*				
5.3%	7.7%	0.69	90%	15%	5000
5.2%	7.7%	0.67			4500
5.1%	7.7%	0.65			4000
4.9%	7.7%	0.63			3500
4.7%	7.7%	0.60			3000

\* The VKA event rate is based on the pooled RE-COVER and RE-COVER II analysis of the oral treatment period [[P13-09153](#), [U12-3306-01](#)]. The Freedman formula was used for the calculations.

In combination with additional non-statistical considerations, a total sample size of up to 5000 patients (i.e., 2,500 patients per group) is deemed appropriate for the planned analyses for [Objective 2](#) on an exploratory basis. The actual power of the analysis will be dependent upon the actual rates of major bleeding and loss to follow-up in the current study, the covariates included in the statistical model, their degree of imbalance between the treatment groups, their strength of association with the outcome, and the use of propensity score matching, and may therefore be different.

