## 9.2 SETTING

It is planned that approximately 6000 patients will be enrolled for [Objective 1](#) and up to 5000 patients will be enrolled for [Objective 2](#) from approximately 300 sites around the world.

[figure not shown]

Figure 9.2:1 Enrollment of patients into the study

Participating countries require the approval of dabigatran etexilate for the VTE indication prior to study initiation within that country. Selected sites should include those physicians (e.g., specialists and general practitioners) and facilities (e.g., general practice offices, specialist offices, hospitals, outpatient-care centers and anticoagulation clinics) that reflect the clinical practice within that country. A robust site feasibility process will be undertaken to ensure that the participating sites represent the standard of care within that country. A pre-screening log will record minimal information about all potential patients (e.g., all patients who present with a VTE, age and gender will be collected if permissible by local law and if patient provided consent to participate in the study). This log will be maintained in the Investigator site file (ISF).

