#### Selection bias:

Selection bias could occur at both the site level and the patient level. If sites where dabigatran etexilate is used frequently differ systematically with respect to patient or the routine procedures from sites that use dabigatran etexilate less frequently, the between site difference could lead to non-comparability between the dabigatran etexilate patients. To minimize the site level selection bias, a robust site feasibility process will be performed to ensure that the participating centers that have access to all available treatment options for VTE that are approved for use in that country and that those physicians follow the standard of care that is accepted within the country.

Selection bias at the patient level could occur if sites preferentially enroll specific patients into the study. To minimize selection bias at the patient level, at a minimum, dabigatran etexilate and VKA treatment options must be available. Consecutive unselected enrollment of patients will be used for the recruitment of patients into [Objective 1](#) which will address issues associated with preferential patient selection by the site staff however; this could potentially create other sources of bias. A balanced approach for enrollment will be used for [Objective 2](#). The balanced approach will also minimize effects of potential temporal changes in prescribing patients, as dabigatran etexilate and VKA patients are enrolled in similar time periods.

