6.5 POOLING OF CENTERS

Centre will not be used as a variable in any analysis; therefore this section is not relevant.

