7. PLANNED ANALYSIS

Summary statistics for continuous variables will include the number of observations (N), mean, standard deviation (SD), minimum, Q1 (25th percentile), median, Q3 (75th percentile), and maximum; tabulations of categorical variables will present all possible categories and will display the number of observations per category as well as percentages. The default precision for percentages should be one decimal place, unless otherwise specified. In general, percentages will be based on all patients in the analysis population, whether they have missing data or not. A category 'Missing' will be displayed whenever at least one patient falls within this category. For variables based on nested questions (i.e. questions which ask for more detailed information only within the subgroup of patients with a specific value for another higher level question), percentages will be based on the patients with the corresponding value for the higher level question.

Individual patient listings will be created, which generally will be sorted by anticoagulation treatment at baseline, region, country, center number and subject number, and be based on the analysis population used for the corresponding table.

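### The Objective 1 precision table assumes independent patients; with about 20 patients per site, its widths are probably too narrow for treatment choice, and the available SAP text specifies no intervals

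*Protocol*

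**What the plan says.** Protocol 9.5 sets the size of Objective 1: "It is planned that a total of approximately 6000 patients will be enrolled". It states that this number does not come from a formal calculation. It promises that baseline characteristics will be reported with estimates and confidence intervals, overall and by category, and adds: "Categorical attributes will be estimated with the precision (i.e., width of descriptive 95% CI) described in Table" 9.5:1. The table's footnote reads "Calculations are based on the Clopper-Pearson method". The worked example takes a 40% attribute and 2000 patients and concludes that "this proportion can be estimated with a precision of 4.34% (i.e. width of 95% CI"). A second example takes a subgroup of 1000 and gives 6.17%.

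Protocol 9.2 says the patients will come "from approximately 300 sites around the world", and 9.1 asks for consecutive enrolment within site. Protocol 9.3.2 and SAP (Objective 1) 5.1 list the primary attributes: age, gender, event type and treatment for the event.

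SAP (Objective 1) 6.5 says: "Centre will not be used as a variable in any analysis; therefore this section is not relevant". SAP (Objective 1) 7 says that tabulations of categorical variables "will display the number of observations per category as well as percentages"; section 7.6 describes the main analyses as descriptive summaries. Section 4, on changes to the planned analysis, mentions only the interim analyses.

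**The concern.** A Clopper-Pearson width is a binomial width: it treats each patient as a separate, independent draw. Patients at one site share prescribers and, often, a formulary and payment arrangements. If they resemble each other in the treatment they receive, 6000 patients carry less information about treatment patterns than 6000 independent patients would.

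The protocol's own account makes such resemblance plausible. Sites range from general practices to hospitals and anticoagulation clinics (9.2). Cost and access are named as drivers of treatment patterns (7.3). The limitations section considers what follows "If sites where dabigatran etexilate is used frequently differ systematically" from other sites, though it treats this as possible selection bias and not as a matter of variance.

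Objective 1 has no hypothesis test, so the precision table is its only quantitative performance claim. If within-site correlation is ignored, intervals for treatment patterns would look more certain than they are. This matters most by region, because a region is made up of whole sites.

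**Working it through.** **Inputs from the documents.** n = 6000 (9.5); about 300 sites (9.2); full width of a two-sided 95% Clopper-Pearson interval (9.5 and the table footnote). Mean cluster size m = 6000 / 300 = 20.

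**Input that must be assumed.** The ICC. The documents give none, so a range of 0.01 to 0.20 is used.

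**Step 1: reproduce the table.** With x = p × n, the limits are the 2.5% quantile of Beta(x, n − x + 1) and the 97.5% quantile of Beta(x + 1, n − x). Of 36 cells, 35 agree with the printed width to within 0.01. For example, 40% and n=2000 gives 4.34, and 50% and n=6000 gives 2.55 against 2.54 printed. The exception is 30% and n=3000: printed 3.28, Clopper-Pearson 3.31. The printed value is the Wald width, 2 × 1.96 × √(0.3 × 0.7 / 3000) = 3.28 points. The difference is about 1% and immaterial. Since n and p alone reproduce the table, it contains no allowance for clustering.

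**Step 2: allow for clustering, all patients.** Design effect DE = 1 + (m − 1) × ICC = 1 + 19 × ICC; effective sample size = 6000 / DE; then the Clopper-Pearson width at that size for p = 50%. The last column is the coverage of an interval that ignores clustering, 2Φ(1.96/√DE) − 1.

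| Assumed ICC | DE | Effective n | Width (points) | Coverage of nominal 95% |
|---|---|---|---|---|
| 0 | 1.00 | 6000 | 2.54 (as printed) | 95% |
| 0.01 | 1.19 | 5042 | 2.78 | 93% |
| 0.05 | 1.95 | 3077 | 3.56 | 84% |
| 0.10 | 2.90 | 2069 | 4.35 | 75% |
| 0.20 | 4.80 | 1250 | 5.62 | 63% |

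**Step 3: unequal site sizes.** With DE = 1 + ((1 + CV²) × m − 1) × ICC and an assumed coefficient of variation of 1.0, DE at ICC 0.05 is 1 + 39 × 0.05 = 2.95, and the width is 4.39 instead of 3.56.

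**Step 4: the protocol's subgroup example** (40%, n=1000, printed 6.17), at ICC 0.05. The result depends on how many sites contribute:

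- From 50 sites of 20, as a region might be: DE = 1.95, effective n = 1000 / 1.95 = 513, width 8.65.
- Spread over all 300 sites, m = 1000 / 300 = 3.33: DE = 1 + 2.33 × 0.05 = 1.117, effective n = 896, width 6.52.

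**Step 5: compare protocol and SAP on intervals.** Protocol 9.5 promises confidence intervals. The available Objective 1 SAP text lists N, mean, SD, quartiles, counts and percentages (section 7) and descriptive summaries (7.6). The abbreviation CI is defined in section 2, but no interval is specified in that text. Sections 6.4 and 7.7 are not in the public document.

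**The case against.** The strongest reply is that nothing here is miscalculated and little depends on it. The table reproduces, the 6000 does not rest on it, and protocol 9.7.1 calls the analyses descriptive and the intervals explorative. That stands: this is a question about a modelling assumption, and no test or sample size fails.

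Second, the size rests entirely on an assumed ICC. At 0.01 the change from 2.54 to 2.78 is of little practical importance, and at zero the table is right. A reader might infer that the precision is overstated for every attribute, or that treatment is largely decided by the site. The documents support neither. Treatment choice is left to the participating physicians (9.3.1.1), the selection-bias text is conditional and is followed by a feasibility process meant to ensure access to the approved options, and nothing suggests that age or sex clusters strongly. What remains is that correlation within site is plausible for treatment.

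Third, a reader might infer that the missing intervals make the stated precision wrong, or that none will be reported. Neither follows. The omission is a separate mismatch between protocol and SAP, and an interval could be specified in the two sections that are not public. If no interval is published, the coverage figures above describe nothing that appears in print.

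Fourth, analysis by region removes between-region differences from the site variance, and sites are selected for feasibility rather than drawn at random, so a site-clustered variance is one defensible choice among several. Both are fair. The regional argument also works the other way: within a region the cluster size does not shrink, as step 4 shows.

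**Conclusion.** Table 9.5:1 is arithmetically right under independence, apart from one immaterial cell. With about 20 patients per site and positive within-site correlation, its widths are too narrow. That is likely for treatment for the index event and uncertain, possibly slight, for age and sex. The size cannot be fixed from the documents: at 50% and n=6000, widths grow by a factor of about 1.09 at ICC 0.01 to 2.19 at ICC 0.20, assuming equal site sizes. For the subgroup of 1000 at ICC 0.05, the increase runs from 6.17 to 6.52 if spread over all sites and to 8.65 if drawn from 50 sites. Separately, the intervals promised in protocol 9.5 are not specified in the available Objective 1 SAP. Both points are worth correcting because the correction is cheap; neither threatens the objective.

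**What to change.** In protocol 9.5, restate Table 9.5:1 over a range of ICCs with about 20 patients per site, or add a footnote that the widths assume no within-site correlation. Correct the 30%, n=3000 cell at the same time.

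In the Objective 1 SAP, specify 95% confidence intervals for the primary attributes, above all treatment for the event, overall and by region. Use a site-clustered variance, such as a sandwich or survey estimator with site as the cluster, and amend 6.5 so that centre may serve as the cluster identifier. If intervals are already specified in the sections that are not public, only the variance method needs adding.

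The cost is somewhat wider intervals and a little programming. Section 7 already sorts listings by centre number, so no new data are needed, and the sample size is unchanged.
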